Antimicrobial efficacies of probiotics and xylitol mouth rinses have not been compared till date. Also their effects on the young and elderly population have not been compared. Hence the purpose of the present study is to compare the antimicrobial efficacies of probiotic and xylitol mouth rinses with the gold standard in children and elderly population.

Aim of the study:

To compare the antimicrobial efficacy of probiotic and xylitol mouth rinses with chlorhexidine (gold standard) among children and elderly population at high risk for dental caries.

Objectives of the study:

1. To assess *Streptococcus mutans* levels at baseline and 14 days after intervention in children and elderly population.
2. To compare efficacies of the 3 mouth rinses in reducing *Streptococcus mutans* levels in children and elderly.

Materials and methods:

Source of data: Residential school children aged 5-12 years at high risk for caries. Elderly population above 60 years residing in old age homes at high risk for caries.

Eligibility Criteria:

Inclusion Criteria:

1. Children aged 5-12 years at high risk for caries.
2. Elderly citizens (above 60 years) at high risk for caries.
3. Those willing to participate in the study and consented.
4. Not under antimicrobial therapy or used probiotic products during past 1 month.

Exclusion Criteria:

1. Using mouth rinse routinely.
2. Undergoing any dental treatment during the study period.
3. Not able to brush their teeth and rinse on their own.

Study Design: Double Blind Randomized Controlled Trial.

Sample Size: Twelve participants will be chosen per group. With 3 products involved in each of the 2 population groups (children and elderly) the sample size will be 36 child participants and 36 elderly participants.

Consent from participants: Permission to conduct the study in the residential school and old age home will be obtained from the concerned authorities. Details about the study will be presented to the participants in the form of a study information sheet or communicated verbally in both English and in the local language. Only the eligible participants who provide written

consent will be included in the study. In case of children, written consent will be obtained from the guardians.

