1 ml saline will be added to the eppendorf tube and vortexed for even distribution of plaque. This mixture will be used as stock solution for serial dilutions. From the stock solution, 100 μ l will be transferred to a sterile test tube containing 900 μ l of saline and vortexed to arrive at 1:10 dilution. Similar dilutions will be prepared to obtain 1/10, 1/100 and 1/1000 dilutions. 50 μ l from each of the dilutions will be plated onto the selective medium MSB (Mitis Salivarius Bacitracin Agar) by spread plate method. After plating, the MSB (Mitis Salivarius Bacitracin Agar) agar plates will be placed in the anaerobic jar and incubated at 37 degree Celsius for 72 hours.

Colonies of *Streptococcus mutans* will be identified based on the following morphologic characteristics, a) 0.5 mm raised convex undulated colonies b) light blue colour with rough margins c) granular frosted glass appearance. The colonies will be confirmed by a catalase test (negative catalase reaction) and gram staining (gram positive cocci). Bacterial colonies will be counted manually. The standard formula for determining Colony Forming Units (CFU) will be $CFU/g = [Number\ of\ colonies \times Dilution\ factor] / [Volume\ plated\ (in\ ml) \times Amount\ of\ plaque\ (in\ g)]$

3. Randomization and Group allocation: After data collection at baseline, the study participants will be allocated to three groups, Group A, B and C, by simple random sampling (lottery method). Group A will be given Chlorhexidine mouth rinse; Group B will be given Xylitol mouth rinse and Group C Probiotic mouth rinse. The participants and the investigator will be blinded from the allocation sequence.

4. Intervention: The participants will be asked to rinse their mouth once daily (at night) for 2 minutes, using 15 ml of mouth rinse. The intervention will be carried out for a period of 14 days. Mouth rinsing will be supervised during the study period by an assistant. A record will be maintained to document regular usage of the mouth rinse and also to record any adverse effects occurring during the intervention period.

5. Post intervention data collection: After 14 days of using the mouth rinses, the same procedures will be repeated and compared with baseline.

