Statistical Analysis Plan: Data will be analysed using SPSS (Statistical Package for the Social Sciences Version 22.0; SPSS Incorporated, Chicago, Illinois). Comparisons before and after interventions will be done using Paired t Test. Comparisons between Chlorhexidine, probiotic and xylitol groups will be done using ANOVA (Analysis of Variance) and Tukey's Post Hoc Tests. Comparison of antimicrobial efficacy of mouth rinses between children and elderly will be done using Independent sample t Test. Statistical significance will be fixed at $p \leq 0.05$.

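### The three-rinse ANOVA names no response or scale and does not use the pre-allocation baseline count as a covariate; a pre-stated ANCOVA on log10 CFU/g would be a cheap improvement.

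*Combined protocol and SAP*

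**What the plan says.** - **Test.** The Statistical Analysis Plan gives the rinse comparison in one sentence: "Comparisons between Chlorhexidine, probiotic and xylitol groups will be done using ANOVA (Analysis of Variance) and Tukey's Post Hoc Tests". It states no response variable, scale or covariate, and does not say whether the test is run in each population or pooled. On the level it says "Statistical significance will be fixed at" p ≤ 0.05.
- **Hints at the response.** The second objective is "To compare efficacies of the 3 mouth rinses in reducing" *S. mutans* levels, and step 5 of the Method says "After 14 days of using the mouth rinses, the same procedures will be repeated and compared with baseline". Both lean toward change from baseline; neither defines the ANOVA response.
- **Baseline.** Step 3 of the Method begins "After data collection at baseline, the study participants will be allocated to three groups", so the count precedes allocation. The Statistical Analysis Plan uses it explicitly only in the paired before/after t test, which does not compare rinses.
- **Scale.** Step 2 of the Method defines the outcome as CFU per gram of plaque. "Similar dilutions will be prepared to obtain 1/10, 1/100 and 1/1000 dilutions", and 50 μl of each is plated. No log transformation and no rule for plates without colonies is given.
- **Size.** There are twelve per group: "With 3 products involved in each of the 2 population groups (children and elderly) the sample size will be 36 child participants" and as many elderly.
- **Age comparison.** "Comparison of antimicrobial efficacy of mouth rinses between children and elderly will be done using Independent sample t Test", again with no response named.

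**The concern.** The aim is to compare xylitol and probiotic with chlorhexidine, and this ANOVA is the only planned test that does so. As written, day-14 or change, and raw or log counts, would all fit the sentence, so the choice could be made after the data are seen. With 12 per arm the choice can alter the result. The baseline count is a legitimate covariate already collected by the trial, and neither ANOVA estimates its slope from the data. How much that costs depends on the SDs at the two times and their correlation, which the documents do not give.

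**Working it through.** **The plan's own figure.** 12 × 3 = 36 per population and 36 × 2 = 72 in all; the arithmetic agrees. The 12 itself cannot be reproduced, because no effect size, SD or power is stated.

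**Inputs.** From the documents: three arms, 12 per arm in each population, 5% level, Tukey tests. Assumed: normal log10 data with a common slope, no detection floor, no dropout, one arm lower by 1 day-14 SD. Let k = baseline SD / day-14 SD (0.5 to 2) and r = baseline to day-14 correlation (0 to 0.8).

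**Relative variance of a difference between two rinses** (day-14 ANOVA = 1):
- change ANOVA: 1 + k² − 2rk
- ANCOVA: (1 − r²) × 32/31 on average, the 32/31 being the cost of estimating the slope

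At k = 1, r = 0.5, change gives 1 + 1 − 1 = 1 and ANCOVA gives 0.75 × 32/31 = 0.774, which is like 12/0.774 = 15.5 per arm. ANCOVA breaks even with day-14 ANOVA when r² = 1/32, so r = 0.177 for any k. Change is more precise than ANCOVA only for r of about 0.33 to 0.64 at k = 0.5, 0.55 to 0.81 at k = 0.7 and above 0.94 at k = 1, and never at k = 1.4 or 2.

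**Power for one Tukey pair.** For day-14 ANOVA the critical value is 3.470/√2 = 2.454 on 33 df and the noncentrality is √(12/2) = 2.449, so power is about one half. Simulation with 40,000 trials per setting gives:

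| k | r | Day-14 ANOVA | Change ANOVA | ANCOVA |
|---|---|---|---|---|
| 1 | 0 | 51% | 25% | 49% |
| 1 | 0.3 | 50% | 36% | 53% |
| 1 | 0.5 | 51% | 51% | 63% |
| 1 | 0.7 | 51% | 76% | 82% |
| 0.5 | 0.5 | 51% | 65% | 63% |
| 0.7 | 0.7 | 51% | 83% | 82% |
| 1.4 | 0.5 | 51% | 32% | 63% |
| 2 | 0.5 | 50% | 16% | 63% |

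**Worst case over 25 settings** (k = 0.5, 0.7, 1, 1.4, 2; r = 0, 0.3, 0.5, 0.7, 0.8). With Tukey-type adjustment of the adjusted means, ANCOVA loses at most 1.7 points to the better ANOVA. With Bonferroni over all three pairs, the largest loss is 4 to 5 points. With Bonferroni over only the two contrasts with chlorhexidine, its power exceeded both three-pair Tukey ANOVAs in all 25 settings, partly because fewer contrasts are tested.

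**Validity.** Family-wise error under the null was 4.7% to 5.2% for each method.

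**Does the unnamed response matter?** The day-14 and change ANOVAs disagreed on the pair in 17% (k = 0.5, r = 0.3) to 61% (k = 2, r = 0.8) of simulated trials.

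**Scale.** If CFU/g is lognormal with log10 SD 0.5 (assumed; k = 1, r = 0.5), raw-scale power is 15% for day-14 and 9% for change, against 51% for either on log10. At log10 SD 0.3 the raw figures are 28% and 21%. Under these assumptions the scale matters more than the covariate.

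**Where the gain shrinks** (k = 1, r = 0.5). It falls from about 12 points at a difference of 1.0 SD to about 5 at 1.6 SD and under 1 at 2.0 SD. A single colony at the lowest plated dilution is 1 × 10 / (0.05 × plaque weight) = 200 / (plaque weight in g) CFU/g, so there is a floor. With values set to an assumed floor 1 SD below the comparator mean, the three powers are about 39/32/48%; at 0.5 SD below, 27/21/34%.

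**The case against.** The strongest reply is that nothing in the plan is invalid. Either ANOVA holds its error rate, one sentence naming the response would close the gap, and ANCOVA is then an efficiency preference whose benefit rests wholly on assumed SDs, correlation and effect size. Much of this stands. No gain can be claimed for this trial in particular. The case for ANCOVA is that k and r are unknown, its possible loss is small and its possible gain is not.

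A reader might go further in four ways that the documents do not support.
- **That the planned ANOVA is biased or has inflated type I error.** It does not on a suitable scale.
- **That the baseline is ignored altogether.** If the response is change, which the wording leans toward, the baseline enters with slope 1.
- **That ANCOVA can never cost more than about 2 points.** That ceiling needs Tukey-type adjustment of the adjusted means; Bonferroni over three pairs takes it to 4 to 5. Nothing here shows that the planned software gives Tukey-type intervals for covariate-adjusted means.
- **That every participant is sure to have a baseline count.** Step 2 samples a non-carious permanent maxillary first molar, which the Eligibility Criteria do not require.

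It is also fair that separate analysis by population is the natural reading of the Sample Size section. It only needs to be stated; pooling at 24 per arm would lower the worst Tukey-type loss to about 0.8 points.

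**Conclusion.** The point holds as a matter of pre-specification and efficiency, and should be acted on. From the text alone, the only between-rinse test lacks a response and a scale and does not use the pre-allocation count as a covariate. The size is conditional on the assumptions listed above. ANCOVA gains about 12 points at k = 1, r = 0.5, gains nothing over day-14 ANOVA when r is near 0, and gains less for larger effects or with many samples at the detection floor. Its greatest loss is about 2 points (Tukey-type) or 4 to 5 (Bonferroni over three pairs). Confidence in the gap is high; confidence in the size of the gain is only moderate. The choice of log10 over raw CFU/g deserves equal weight.

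**What to change.** Add to the Statistical Analysis Plan, before the data are seen:
1. The main rinse comparison, run separately in children and in elderly: ANCOVA of log10 day-14 CFU/g on rinse group (three levels) and log10 baseline CFU/g, with adjusted differences from chlorhexidine and their confidence intervals.
2. The multiplicity method for the adjusted means: either Tukey-type over three pairs, after confirming that the software provides it, or Bonferroni over the two contrasts with chlorhexidine, which match the aim.
3. A rule for no-colony samples (CFU/g of 0 has no logarithm), their number by arm, and a sensitivity check of the rule.
4. A rule for a missing baseline count.
5. A sensitivity check of linearity and a common slope.
6. The response for the children-versus-elderly t test. Those groups are not randomised, so this ANCOVA is not proposed for that comparison.

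If the investigators prefer ANOVA, the minimum is to name the response (for example, change in log10 CFU/g) and the log10 scale in advance.

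**Cost.** A few sentences; no new participants, samples or visits. ANCOVA uses one residual degree of freedom (32 instead of 33), assumes a roughly linear common slope, and carries the small power losses given above.

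### The child-elderly comparison rests on independent t tests alone, and no planned analysis tests whether the randomised differences between rinses depend on age group

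*Combined protocol and SAP*

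**What the plan says.** The Statistical Analysis Plan is one paragraph. It has paired t tests for before versus after. For the rinses: "Comparisons between Chlorhexidine, probiotic and xylitol groups will be done using ANOVA (Analysis of Variance) and Tukey's Post Hoc Tests". For age: "Comparison of antimicrobial efficacy of mouth rinses between children and elderly will be done using Independent sample t Test". Rinse is the only factor named for the ANOVA, and neither a two-way model nor a rinse-by-age term appears anywhere.

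The age question is part of the rationale. Need for the study says of the probiotic and xylitol rinses: "Also their effects on the young and elderly population have not been compared". It is not one of the two numbered objectives.

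The populations are described under Source of data: "Residential school children aged 5-12 years at high risk for caries. Elderly population above 60 years residing in old age homes". Under Sample Size, "the sample size will be 36 child participants and 36 elderly participants". All three arms are active (Randomization and Group allocation): "Group A will be given Chlorhexidine mouth rinse; Group B will be given Xylitol mouth rinse and Group C Probiotic mouth rinse". Use is overseen (Intervention): "Mouth rinsing will be supervised during the study period by an assistant". The outcome is left at this (Post intervention data collection): "After 14 days of using the mouth rinses, the same procedures will be repeated and compared with baseline".

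**The concern.** The plan presents the t test as a comparison of rinse efficacy between ages, but it compares two populations that differ in far more than age. They live in different institutions and may start at different *Streptococcus mutans* levels. Their counts may also drift differently over 14 days for reasons such as supervision, brushing or diet. No inactive arm exists to remove that drift. A significant result would be read as a rinse working differently in children and the elderly when it may reflect who they are and where they live.

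Randomisation does protect one age question, whether the differences between rinses change with age, and that question is not tested. Running the ANOVA separately in each population would not fill the gap, because comparing two sets of p-values is not a test of interaction.

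The plan also leaves open which outcome enters the t test (raw change, log change, day-14 level), whether it is run per rinse (12 v 12, three tests) or pooled (36 v 36), and how multiple tests are handled.

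**Working it through.** **The plan's own figure.** 12 × 3 rinses = 36 per population, and 36 × 2 = 72, as stated: six cells of 12. The 12 cannot be derived, because no SD, effect size or power is given.

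**What each analysis estimates.** Write the mean change in age group *a* on rinse *k* as c(a) + e(a,k), where c is non-specific change and e is the rinse effect.

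- Per-rinse t test: [c(child) − c(elderly)] + [e(child,k) − e(elderly,k)]. With no inactive arm the two brackets cannot be separated.
- Rinse contrast within one age group: e(a,k) − e(a,j). Here c cancels.
- Interaction: the child contrast minus the elderly contrast. Here c cancels again.

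**Assumptions for the sizes** (none is in the documents): normal log10 counts, a 1 log10 reduction in both ages unless stated, before-after correlation r = 0.5, SD 0.5 or 0.8, no dropout, two-sided p ≤ 0.05. Each setting had 20,000 simulated trials (Monte Carlo error at most √(0.25/20,000) = 0.35 points).

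**1. Different starting levels only.** Baselines are 0.5 log10 apart and the log reduction is equal. Entries are t-test rejection rates at SD 0.5 / SD 0.8.

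| Outcome tested | 12 v 12 | 36 v 36 |
|---|---|---|
| Raw change | 33% / 7% | 80% / 22% |
| log10 day-14 | 65% / 30% | 99% / 74% |
| log10 change | 5% / 5% | 5% / 5% |
| Percent reduction | 3% / 2% | 4% / 3% |

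A baseline gap distorts raw change and day-14 level but drops out of log10 change, so the unstated outcome decides the answer.

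**2. Non-specific age shift in log10 change, identical rinse contrasts.**

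| Shift (log10) | Any of three tests | Pooled test | Interaction, 2 and 65 df |
|---|---|---|---|
| 0.1 | 21% / 17% | 13% / 8% | 5% |
| 0.25 | 52% / 30% | 55% / 25% | 5% |
| 0.5 | 96% / 67% | 99% / 74% | 5% |

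Hand check: SD of change = SD × √(2(1 − r)) = SD, so 0.25 at SD 0.5 is 0.5 SD. Noncentral-t power for 12 v 12 is then 0.215, and 1 − (1 − 0.215)³ = 0.516. In 51% / 30% of all trials at shift 0.25 only some of the three tests are significant, a pattern easily misread as rinse-specific age dependence.

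**3. No difference at all.** Three tests at 0.05: 1 − 0.95³ = 14%. Pooled: 5%.

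**4. The reverse failure.** With child-elderly differences of +0.8, −0.8 and 0 SD for the three rinses, the pooled t test rejects in 3% of trials and the interaction test in 68%.

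**5. Limits of the interaction test.** For one rinse contrast compared between ages, SE = √(4/12) × residual SD = 0.577 × residual SD. The difference detectable with 80% power is (t₀.₉₇₅ + t₀.₈₀ on 65 df) × 0.577 = 1.64 residual SD. Residual SD = SD × √(1 − 0.5²), which is 0.433 or 0.693. That gives 0.71 log10 (about 5-fold) or 1.14 log10 (about 14-fold). If the three rinses are equally effective and all are half as effective in the elderly, the interaction still rejects only 5%. If they are unequal, halving does create an interaction: with reductions in children of 1.5, 1.0 and 0.5 log10 it rejects in about 39% / 18%.

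**6. Adjusting the age effect for baseline.** With baselines 0.5 apart and no age difference in change, the baseline-adjusted population effect is 0.5 − 0.5 × 0.5 = 0.25 log10. This spurious effect is significant in 57% / 30% of trials, against 5% / 5% for a pooled t test on log10 change.

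**The case against.** The strongest reply is that the interaction answers a different question. The plan asks how the rinses do in one age group against the other, and a direct comparison addresses that, if not causally. Under equal halving in the elderly, the three per-rinse t tests on log10 change give at least one significant result in 95% / 67% of trials, and the pooled test in 99% / 75%, where the interaction gives 5%. This stands as a reason to keep the direct comparison. It does not rescue its interpretation. Halving a 1 log10 effect is a 0.5 log10 difference in change, and a purely non-specific 0.5 shift gives practically the same rates (96% / 67% and 99% / 74%). The t test cannot tell the two apart.

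Every input is assumed, and nothing in the documents shows that drift differs by age. That stands, so the rates illustrate and do not predict. At a shift of 0.1 most of the 21% / 17% is the 14% multiplicity rate; confounding adds about 7 / 3 points. Log10 change and percent reduction are natural readings of efficacy, and under them the baseline-gap problem vanishes. That is also true, but the plan names neither.

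The unnamed outcome, the per-rinse or pooled choice and the missing multiplicity rule are separate omissions that an interaction term does not repair. That stands too, and the fix has to cover each. Finally, the age comparison is not a numbered objective and the added test is weak. Both limit the importance of the point without removing it.

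**Conclusion.** The concern holds. The plan gives the age comparison to t tests on an unrandomised factor tied to setting, with no inactive arm, and plans no test of whether rinse differences depend on age. The textual gap is certain; the size is conditional on the assumed SDs, correlation and shifts. With a non-specific shift of 0.1 to 0.5 log10 and identical rinse contrasts, the per-rinse reading gives at least one significant test in 21% to 96% of trials at SD 0.5 and 17% to 67% at SD 0.8. The pooled reading gives 13% to 99% and 8% to 74%. The interaction test stays at 5%.

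This should be changed, but it does not threaten the main result: the randomised comparison of rinses within each age group is not affected.

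**What to change.** Amend the Statistical Analysis Plan as follows.

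- Analyse log10 CFU/g.
- Fit one model to all 72 participants: log10 day-14 count on log10 baseline, rinse, population and rinse × population. Use the 2-df interaction, labelled exploratory, to test whether rinse differences depend on age.
- Report xylitol versus chlorhexidine and probiotic versus chlorhexidine within children and within the elderly, with 95% confidence intervals.
- Keep the direct child-elderly comparison as a descriptive, unrandomised comparison of log10 change with a 95% confidence interval. State whether it is per rinse or pooled, and do not attribute it to the rinse. If per rinse, say how the three comparisons are handled.
- Do not use the baseline-adjusted population main effect for that purpose.
- State that a null interaction does not show equal absolute efficacy in the two age groups.

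The cost is SAP wording and one extra model on data already planned. The drawback is low power at 12 per cell: the interaction will often be inconclusive and should be reported as such, with emphasis on the estimates and intervals.
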